## **10.2. Prior and New Concomitant Medications**

Verbatim terms on eCRFs will be mapped to Anatomical Therapeutic Chemical (ATC) class and Preferred Name using the WHO Drug Dictionary Enhanced.

Pretreatment concomitant medications are those medications with start and stop prior to the initial dose of investigational product also classified as no concomitant medication. Prior concomitant medications are those medications started prior to and continued after the initial dose of investigational product. New concomitant medications are those medications that were started after the initial dose of investigational product. If it cannot be determined whether the medication was a new concomitant medication due to a partial start or stop date or if the medication is taken on the same date as the initial dose of investigational product, then it will be counted as a new concomitant medication.

No concomitant, prior, and new concomitant medications will be summarized separately for each treatment group by WHO ATC level 2, WHO ATC level 4, and preferred name using the Safety Population. These summaries will present the number and percentage of subjects using each medication. Subjects may have more than one medication per ATC level and preferred name. At each level of subject summarization, a subject is counted once if he/she reported one or more medications at that level. Each summary will be ordered by descending order of incidence of ATC level and preferred name within each ATC level.

Extent of exposure of newly initiated use (after the 1st dose) of vitamin E, thiazolidinediones, bile acid sequestrants (BABR), statins and other lipid-lowering medications, will be calculated as follows:

$$\text{Exposure to the concomitant medication} = \{[(\text{Date of last dose} - \text{Date of 1}^{\text{st}} \text{ dose}) + 1] - \text{Total duration of temporary interruptions}\}$$

Missing start and end dates will be imputed as described in [Appendix A](#). Extent of exposure will be summarized by treatment group as described in the General Statistical Methods ([Section 4](#)).

### 10.3. Adverse Events

AE data will be collected from the time that signed informed consent is obtained until the subject fully completes her/his study participation of the study. AEs will be reported and categorized using the Common Terminology Criteria for Adverse Events (CTCAE, Version 4.03).

All AE summaries will be restricted to TEAEs, which are defined as any AEs that newly appear, increase in frequency, or worsen in severity following randomization up to 30 days from the last dose date of permanent investigational product discontinuation up to new data cut-off date. If it cannot be determined whether the AE is treatment emergent due to a partial onset date, then it will be counted as such. Verbatim terms on eCRFs will be mapped to preferred terms (PT) and system organ classes (SOC) using MedDRA version 18.1 or later version.

Each AE summary will be displayed by treatment group. Summaries that are displayed by SOC and PT will be ordered by descending order of incidence (OCA 25 mg, followed by OCA 10 mg, followed by placebo) of system organ class and preferred term within each system organ class. Summaries of the following types will be presented:

- Overall summary of TEAEs
- Subject incidence of TEAEs and the total number of entries by MedDRA SOC and PT.
- Subject incidence of TEAEs and the total number of entries by PT in descending order.
- Subject incidence of serious TEAEs and the total number of entries by MedDRA SOC and PT.
- Subject incidence of TEAEs leading to investigational product withdrawal by MedDRA SOC and PT.
- Subject incidence of TEAEs leading to study discontinuation by MedDRA SOC and PT.
- Subject incidence of TEAEs by MedDRA SOC, PT, and highest severity (CTCAE grade). At each level of subject summarization, a subject is classified according to the highest severity if the subject reported 1 or more events. AEs with missing severity (CTCAE grade) will be considered grade 3 (severe) for this summary.
- Subject incidence and total number of entries of CTCAE grade 3 or higher TEAEs by MedDRA SOC and PT. At each level of subject summarization, a subject is

classified according to the highest severity if the subject reported 1 or more events. AEs with missing severity (CTCAE grade) will be considered grade 3 (severe) for this summary.

- Subject incidence and total number of entries of related TEAEs by MedDRA SOC and PT. At each level of subject summarization, a subject is classified according to the closest relationship to investigational product if the subject reported 1 or more events. TEAEs with a missing relationship will be considered related for this summary.
- Subject incidence and total number of entries of related CTCAE grade 3 or higher TEAEs by MedDRA SOC and PT. At each level of subject summarization, a subject is classified according to the highest severity if the subject reported 1 or more events. AEs with missing severity (CTCAE grade) will be considered grade 3 (severe) for this summary. TEAEs with a missing relationship will be considered related for this summary.
- Subject incidence of TEAEs occurring by MedDRA SOC and PT with frequency at least 5% within any treatment group.
- Subject incidence of TEAEs by MedDRA SOC, PT, and closest relationship to biopsy (Related/Not Related). At each level of subject summarization, a subject is classified according to the closest relationship to biopsy if the subject reported 1 or more events. AEs with a missing relationship will be considered related for this summary.
- Subject incidence of TEAEs leading to death and the total number of entries by MedDRA SOC and PT

The following listings will be presented by treatment group and subject:

- All TEAEs
- Serious TEAEs (This is a subset of the TEAEs where serious is marked as “Yes”)
- CTCAE Grade 3 or higher TEAEs (This is a subset of TEAEs where severity is marked as CTCAE grade 3, 4, or 5)
- Study Drug Related TEAEs (This is a subset of the TEAEs where relationship to study drug marked as “Definite,” “Probable,” or “Possible”)
- Biopsy-related TEAEs (This is a subset of the TEAEs where relationship to biopsy marked as “Definite”, “Probable”, or “Possible”)
- TEAEs leading to Study Drug Withdrawal or Study Discontinuation (This is a subset of the TEAEs where Action Taken with Study Treatment is checked as “Drug Withdrawn” or “Subject Discontinued from Study”)
- TEAEs leading to death (This is a subset of the TEAEs where outcome is indicated as “Fatal” or the CTCAE grade is 5)

## 10.4. Adverse Events of Special Interest

The following treatment-emergent AESIs will be summarized:

- Pruritus
- Hepatic
- Cardiovascular
- Dyslipidemia
- Gallbladder disease and related complications
- Pancreatitis
- Renal
- Urolithiases
- Hyperglycaemia/New onset diabetes mellitus

Each subcategory of interest will be defined using Standardized MedDRA Queries (SMQs) and/or custom MedDRA queries, as specified in the subsequent sections.

AESI analyses will include all of the following:

- Incidence of treatment-emergent AESIs by PT
- Incidence of treatment-emergent AESIs by PT and severity
- Incidence of serious treatment-emergent AESIs by PT
- Incidence of treatment-emergent AESIs leading to IP withdrawal by PT
- Incidence of related treatment-emergent AESIs by PT
- Incidence of treatment-emergent AESIs leading to death by PT
- Exposure-adjusted incidence of AESIs by PT
- Exposure-adjusted incidence of serious AESIs by PT
- Exposure-adjusted incidence of AESIs by baseline diabetes status
- Exposure-adjusted incidence of severe (Grade 3+) AESIs by PT
- KM statistics and plot for time to first onset of treatment-emergent AESI
- KM statistics and plot for time to onset of first severe (Grade 3+) or serious treatment-emergent AESI
- KM statistics and plot for duration of first treatment-emergent AESI
- KM statistics and plot for duration of most severe treatment-emergent AESI
- Percentage of subject-days with treatment-emergent AESIs per subject exposure year (SEY), by severity

All summaries noted above will include crude incidence rates for each level of summation. For overall incidence summary of AESI, analyses will be performed separately for AESI collected on-treatment only and during study.

**Exposure-adjusted incidence rate (EAIR)** difference (with corresponding 95% Cis) will be calculated for the number of subjects with any event by subcategory of interest as well as for each PT. EAIR will be calculated to correct for differences in investigational product exposure by using person-time in the denominator. Adjusted incidence per 100 SEY is defined as the number of subjects with an event for whom person-time is available divided by the total SEY for each treatment group and multiplied by 100. If a subject experiences the event of interest, the subject's SEY will be calculated as (first event onset date, minus the first dose date plus 1) divided by 365.25 days/year. If a subject does not experience the event of interest, the subject's SEY will be calculated as (earliest date of the last dose date plus 30 days or study discontinuation date or death date or date cut-off date minus the first dose date plus 1) divided by 365.25 days/year. One SEY is the equivalent of one subject exposed to investigational product for one year. Two subjects who are exposed to investigational product for half a year together contribute one SEY. The total SEY of a treatment group is the sum of the SEY for each subject in that treatment group. Exposure-adjusted incidence rates will be calculated for each treatment group. Exposure-adjusted incidence rate difference and the corresponding 95% CI will be derived from Poisson regression model with treatment as explanatory variables.

The time to onset of first treatment-emergent AESI, including onset of first treatment-emergent AESI with different categories, will be estimated using the KM method by calculating the time from the first dose date to the first occurrence of a specific category of treatment-emergent AESI. Subjects who do not experience an event will be censored as described in General Statistical Methods ([Section 4](#)).

The duration of first treatment-emergent AESI and most severe treatment-emergent AESI will be estimated using the KM method by calculating the time from the start date of first occurrence of a given treatment-emergent AESI or most severe AESI to its resolution (AE outcome being "recovered/resolved" in the eCRF). If the AESI remains ongoing, subjects will be censored as described in General Statistical Methods ([Section 4](#)). Only subjects with the events will be included in the analysis.

KM estimates will be plotted as a "survival curve" for each treatment group, with the number at risk identified. In addition, time-to-event data will be summarized with descriptive statistics for those with an event.

A by-subject data listing will be provided for AEs of special interest (AESI) by category including the Standardized MedDRA query (SMQ) where applicable.

Specific analyses for each AESI will be described in the subsequent sections.

#### **10.4.1. Pruritus**

Treatment-emergent pruritus, defined as any preferred term within the pruritus Not Elsewhere Classified (NEC) high level term (HLT) or including "prur," will be summarized separately by the MedDRA SOC, treatment group, and PT as a subset of all TEAEs. Additional summaries of

overall pruritus TEAEs will be provided. These summaries will be generated for the Safety and ITT Populations.

For subjects reporting an AE of pruritus, the various strategies for management of pruritus (listed below) will be summarized (per FDA request). Frequencies per treatment group will be reported. In addition, interruption of investigational product and decreased dose frequency will be summarized and presented in the following ways:

1. each subject represented only once,
2. average interruptions per subject,
3. number of interruptions lasting: 1-5 days, 6-10 days, >10 days.

An analysis of treatment-emergent pruritus event days per patient years on study will be performed. The days at each severity grade, including the total days of event, the total patient years on study, and the event days per patient year on study at each severity grade, including the total, will be summarized. Each individual patient year on study will be derived as (the earliest date of last dose date plus 30 days, study discontinuation date, death date and data cut-off date minus the first dose date plus 1) divided by 365.25 days/year.

Strategies for management of pruritus ( $\leq$  Grade 2 Severity) include:

- Interruption of investigational product
- Decreased dose frequency of investigational product
- Any medication initiated for pruritus
  - bile acid sequestrants
  - antihistamines
  - corticosteroids
  - other (e.g., naltrexone/naloxone, rifampin/rifampicin)
- None of these strategies (no management).
- Two listings of all treatment-emergent pruritus events will be provided: the standard AE listing, and an additional listing which will include the concomitant medication(s) received, adjustments to investigational product dosing frequency or amount, mandatory investigational product interruption, and/or holiday. The time between each event and its preceding one will be presented per subject.

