15.1.6. Reporting of Adverse Events and Serious Adverse Events

15.1.6.1. Reporting of Adverse Events

AE data will be collected from the time that signed informed consent is obtained until the subject fully completes her/his study participation of the study.

All AEs, whether believed by the Investigator to be related or unrelated to the investigational product, must be documented in the subject's medical records, in accordance with the Investigator's normal clinical practice and on the AE CRF. Each AE is to be evaluated for duration, intensity, frequency, seriousness, outcome, other actions taken, and relationship to the investigational product. Redacted medical record source documentation will be requested for all SAEs and emergency room visits.

[figure not shown]
In addition, the Investigator should contact the study Medical Monitor promptly when any signs or symptoms of hepatic decompensation are observed in any subject.

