15.1.11. Follow-Up of AEs and SAEs

All AEs must be followed during the course of the study until the AE resolves, is no longer of clinical concern, has stabilized or is otherwise explained, or the subject is lost to follow-up.

AEs ongoing at the final visit that are deemed to be “possibly, probably, or definitely” related or of other clinical significance must be followed for as long as necessary to adequately evaluate the safety of the subject or until the event stabilizes, resolves, or is no longer of clinical concern.

If resolved, a resolution date for the AE should be documented on the CRF. The Investigator must ensure that follow-up includes any supplemental investigations indicated to elucidate the nature and/or causality of the AE. This may include additional laboratory tests or investigations, or consultation with other healthcare professionals, as considered clinically appropriate by the Investigator.

All subjects showing possible drug-induced liver injury or disease progression should be followed until all abnormalities return to normal or to the baseline state. Drug-induced liver injury may develop or progress even after the causative drug has been stopped. Results should be recorded in the CRF. Note that longer follow-up can sometimes reveal an off-drug repetition of what had appeared to be drug-induced liver injury, indicating that liver injury was related to underlying liver disease.

If a subject experiences symptoms consistent with cholelithiasis or pancreatitis, the subject should have investigational product interrupted while undergoing a complete evaluation for both conditions consistent with local standards of care. If symptomatic cholelithiasis and/or cholecystitis is diagnosed, the subject should be managed and monitored as described in [Section 7.5.1](#).

If a subject is suspected to have acute pancreatitis or develops signs and symptoms consistent with acute pancreatitis, amylase and lipase levels should be monitored for 3 months after the onset of symptoms per local standard of care. If treatment-emergent acute, or nonacute pancreatitis is diagnosed, investigational product must be discontinued, and the subject should be managed and monitored as described in [Section 7.5.2](#). The Investigator should contact the Medical Monitor upon awareness of pancreatitis. Results should be recorded promptly in the eCRF.

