Time-to-event data will be summarized using Kaplan-Meier (KM) methodology using 25th, 50th (median), and 75th percentiles with associated 2-sided 95% CIs, as well as the percentage of censored observations. KM estimates will be plotted as a “survival curve” for each treatment group, with the number at risk identified. In addition, time-to-event data will be summarized with descriptive statistics for those subjects with an event. Subjects who do not experience an event will be censored. Subjects who do not experience an event will be censored at the date of last contact for clinical outcome endpoints and will be censored at the earliest date of last dose date+30 days, end of study, death date or date cut-off date for treatment-emergent adverse events (TEAEs). The censor date for time to resolution events will be the earliest date of end of study, death date or date cut-off date.

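### The pruritus event-day rate in SAP 10.4.1 ends its person-time at last dose plus 30 days but sets no end to the event days, so pruritus that outlasts the drug by more than 30 days overstates the rate, by an amount the documents cannot fix

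*SAP*

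**What the plan says.** SAP 10.4.1 states the measure: "An analysis of treatment-emergent pruritus event days per patient years on study will be performed". The items to be tabulated are "The days at each severity grade, including the total days of event, the total patient years on study", together with the resulting rate, by grade and overall. Person-time for each subject is defined as follows: "Each individual patient year on study will be derived as (the earliest date of last dose date plus 30 days, study discontinuation date". The list of candidate end dates also includes death and data cut-off. The interval is counted from first dose with both end days included, and converted to years of 365.25 days. No end date is given for the event days.

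Four other places bear on how long an event can run:

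- SAP 10.3 defines a treatment-emergent event by when it appears, becomes more frequent or worsens, "following randomization up to 30 days from the last dose date of permanent investigational product discontinuation". That limits onset or worsening. It does not limit duration.
- SAP 4 uses a different clock for duration: "The censor date for time to resolution events will be the earliest date of end of study, death date or date cut-off date".
- Protocol 15.1.6.1: "AE data will be collected from the time that signed informed consent is obtained until the subject fully completes her/his study participation". Protocol 15.1.11 adds: "All AEs must be followed during the course of the study until the AE resolves, is no longer of clinical concern".
- SAP Appendix A imputes partial AE stop dates to the end of the month or year, with no cap at last dose plus 30 days.

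Protocol 7.4.4 and Table 4 require permanent discontinuation of drug for pruritus of Grade 3 or higher. The subject stays in the study and keeps attending visits.

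**The concern.** A rate of days per person-year makes sense only if both parts cover the same calendar window. Here the person-time ends at last dose plus 30 days for anyone who stops drug permanently. The event days, taken from ordinary AE start and stop dates, can run on to resolution or to the end of participation. Each pruritus day beyond the 30-day tail then raises the numerator and adds nothing to the denominator. The label compounds this: it says on study, but the formula gives time on treatment plus 30 days.

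Protocol 5.5 names pruritus as the main adverse event related to OCA and calls it dose dependent, so the table will be read closely by arm and by grade. The Grade 3 or higher row is most exposed, because the protocol ends drug, and so nearly ends person-time, in those subjects while their events are still being followed.

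**Working it through.** **Plan's own figure.** The documents give no expected value for this rate, so there is nothing to reproduce. The check applies the SAP formula directly.

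**Formulas**

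- As written: D / {[min(last dose + 30, study discontinuation, death, cut-off) − first dose + 1] / 365.25}, where D is all event days.
- Matched on-treatment: the same denominator, with D cut at the date that ends it.
- Matched on-study: all event days over the time from first dose to the earliest of study discontinuation, death or cut-off.

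**One subject** (assumed dates: first dose Day 1, onset Day 60, last dose Day 90, resolved Day 270)

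- Denominator: (90 + 30 − 1 + 1) / 365.25 = 120 / 365.25 years.
- As written: (270 − 60 + 1) = 211 days; 211 × 365.25 / 120 = 642 per patient-year.
- Matched on-treatment: (120 − 60 + 1) = 61 days; 61 × 365.25 / 120 = 186.

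Non-overlapping days cannot exceed 365.25 per year, so 642 is not a possible burden.

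**A second subject** (assumed: last dose Day 60, pruritus Day 30 to 300, study end Day 1400)

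- As written: 271 / (90 / 365.25) = 1100.
- Matched on-treatment: 61 / (90 / 365.25) = 248.
- Matched on-study: 271 / (1400 / 365.25) = 71.

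If this subject's pruritus ends by Day 90, the as-written and matched on-treatment rates are identical.

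**Arm level.** From the protocol: 4 years of follow-up (Section 7.1) and pruritus incidence of 23% on OCA and 6% on placebo in the earlier Phase 2 study of 25 mg (Section 5.3). Assumed: 5% of the 25 mg arm and 0.5% of placebo stop drug for pruritus, with last dose on Day 120 and 60 event days before it; other cases have a 60-day episode and stay on drug for 4 years (1461 days). Arm size cancels.

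For 25 mg, with pruritus lasting 90 days after last dose:

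- Person-years per subject: (0.05 × 150 + 0.95 × 1461) / 365.25 = 3.82.
- As written: [0.05 × (60 + 90) + 0.18 × 60] / 3.82 = 18.3 / 3.82 = 4.79.
- Matched on-treatment: [0.05 × (60 + 30) + 0.18 × 60] / 3.82 = 15.3 / 3.82 = 4.00.

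| Days after last dose | Placebo: written / matched on-treatment | 25 mg: written / matched on-treatment | 25 mg: inflation | 25 mg: matched on-study |
|---|---|---|---|---|
| 30 | 0.94 / 0.94 | 4.00 / 4.00 | 1.00 | 3.83 |
| 60 | 0.98 / 0.94 | 4.40 / 4.00 | 1.10 | 4.20 |
| 90 | 1.02 / 0.94 | 4.79 / 4.00 | 1.20 | 4.58 |
| 180 | 1.13 / 0.94 | 5.97 / 4.00 | 1.49 | 5.70 |
| 365 | 1.36 / 0.94 | 8.39 / 4.00 | 2.09 | 8.01 |

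The inflation column is relative to the matched on-treatment rate. Against a true on-study rate the 25 mg excess here is only about 5% (4.79 / 4.58), because only pruritus stops shorten the denominator in this illustration.

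**Grade 3 row.** In the extreme case where every day in that row comes from subjects who stopped, inflation at 90 days is (60 + 90) / (60 + 30) = 1.67, against 1.20 for all grades. It is less if the grade falls after drug is stopped.

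**Between arms.** If the same 20% of pruritus cases stop in each arm, relative inflation at 90 days is 1.18 in both, but the absolute excess is 0.72 days per patient-year on 25 mg and 0.18 on placebo.

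**Simulation range.** These runs use the same incidences, 4 to 8 years of follow-up and lognormal event durations with medians of 60 to 180 days.

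- 30% of OCA cases and 10% of placebo cases stopping, 5 to 20% of events never resolving: inflation of 1.61 to 1.87 on OCA and 1.35 to 1.50 on placebo; the between-arm difference inflates 1.7 to 2.0 fold.
- 5% and 0% of cases stopping, none unresolved: 1.07 to 1.18 on OCA; the difference inflates 1.08 to 1.19 fold. The OCA-to-placebo ratio hardly moves (3.87 against 3.77 matched; 3.92 against 3.76).

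**The case against.** The SAP nowhere says in so many words that event days run past the denominator. A programmer could count only days inside the treatment-emergent window, which shares the 30-day limit, and then there is no mismatch. This is fair, but that window governs onset or worsening, and the SAP's own clock for duration runs to end of study, death or cut-off. The uncapped count is the plain reading; at best, two programmers could produce different tables. The on-study label is wrong for the formula under either reading.

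A reader might infer that the rate, or the difference between arms, is inflated about two fold. The documents do not support that. It needs roughly 30% of OCA pruritus cases to stop drug, which is 0.30 × 23% = 6.9% of the arm, whereas Protocol 5.3 reports a single pruritus discontinuation in the study that supplied the 23%. In another NASH study it reports 0, 0, 2 and 5 stops on placebo, 10, 20 and 40 mg. It also needs long persistence off drug, for which no figure is given; Protocol 5.3 describes pruritus as manageable with medication and treatment interruption.

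A reader might also infer that the arm with more stops is always inflated most in relative terms. That depends on the share of cases that stop, and the equal-share case above shows no difference.

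Finally, this is one descriptive safety line. Incidence by severity, Kaplan-Meier duration and listings cover the same ground, and any error overstates pruritus, which works against the drug. These points limit the consequence. They do not make the formula correct.

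**Conclusion.** The point stands as a mismatch of windows in a descriptive safety rate. Read plainly, SAP 10.4.1 counts event days beyond last dose plus 30 days with no person-time to match, overstates the rate, and can return values above 365.25 days per year for a subject. The label contradicts the formula.

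The size cannot be settled from the documents, because they give no duration of pruritus after drug is stopped. Relative to a matched on-treatment rate, inflation is nil if pruritus ends within 30 days of last dose, about 1.1 to 1.2 fold under low stopping rates, and up to about 2 fold only under high assumed stopping and persistence. The absolute excess is larger in the arm with more pruritus stops if persistence is similar across arms; relative inflation need not differ. No hypothesis test, alpha or sample size is affected. The correction should be made because it is cheap and concerns the main adverse effect of the drug.

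**What to change.** In SAP 10.4.1, use one window for both parts of the rate:

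- **On-treatment (+30 days):** keep the present denominator, cut each event's days at the date that ends it, and relabel the rate.
- **On-study, if wanted:** run the denominator from first dose to the earliest of study discontinuation, death or data cut-off, and count all event days to that same date.

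Apply the rule to each severity grade as well as to the total. The on-treatment version leaves persistent post-drug pruritus out of the rate, so showing both versions is reasonable; SAP 10.4 already separates on-treatment from during-study for the overall incidence of events of special interest.

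The cost is a sentence of SAP text and a small programming change, with no new data. Compared with an uncapped count, the reported rate will be somewhat lower. If truncation was always intended, only the sentence and the label are needed.
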